## **8 STUDY ASSESSMENTS AND PROCEDURES**

### **8.1 SCREENING PROCEDURES**

*Screening activities performed prior to obtaining informed consent*

Minimal risk activities that may be performed before the subject has signed a consent include the following:

- Email, written, in person or telephone communications with prospective subjects
- Review of existing medical records to include H&P, laboratory studies, etc.

Once the research team has identified a potential subject for the study, the subject will be asked to come to the NIH. The study team will consent the subject, allowing time for the subjects to ask questions and make a voluntary decision.

*Abbreviated Title: IQ in sickle cell disease*

*Version Date: May 5, 2023*

Once the subject signs the consent, the following tests will be done at the Screening Visit unless any of the tests have been performed under another NIH protocol 90 day prior to signing the consent (unless otherwise stated).

**Screening Visit:**

- History and physical exam including prior transfusion history
- CBC with differential
- Reticulocyte count
- Acute care panel, Mineral panel, Hepatic panel, total protein, creatinine kinase, uric acid, lactate dehydrogenase
- Calculated creatinine clearance
- Serum HBsAg, anti-HBc, anti-HBs, anti-HCV, anti-HIV
- Coagulation screen (PT/INR, PTT, fibrinogen, D-dimer)
- Pregnancy test (serum or urine) for female subjects and use of barrier methods of contraception for male subjects
- Hemoglobin electrophoresis

Up to 60 subject will sign consent to be screened with the goal of enrolling 46 subjects eligible to participate in the interventional portion of the study.

**8.2 STUDY EVALUATION PROCEDURES**

Study Procedures will be conducted per table in section 1.3 (SOA) and are described below. The effectiveness of IQ in reducing P-selectin levels will be assessed as described in section 9.

**Physical examination and medication history:**

A physical examination, review of medication history, and review of available laboratory tests may be completed on each subject. Medical records obtained under other protocols may also be reviewed. Vital signs and biophysical data (blood pressure, heart rate, respiratory rate, temperature, height, and weight) may also be collected at each visit. These measurements will be made per NIH Clinical Center policies.

Optional exploratory studies of peripheral arterial tonometry and/or NIRS will be based on service availability and may be conducted in patients that agree to this procedure.

**Peripheral Arterial Tonometry (PAT) (ENDO-PAT 2000, Itamar Medical):**

PAT is an FDA-approved noninvasive technology that captures a beat-to-beat plethysmographic recording of the finger arterial pulse wave activity with pneumatic probes, which provides a measure of endothelial function, similar to that of brachial artery ultrasound (BAUS) assessment of flow mediated dilation. It is claimed that this method is highly automated, consistent, and operator independent.

The PAT finger probe consists of a thimble-shaped sensor cap that imparts a uniform pressure fields and exhibits a clamp-like effect on the entire surface of the distal phalanx and measures pulsatile volume changes. PAT applies a significant counter pressure (70 mmHg) on the digit to avoid distal venous distention, thereby inhibiting venous pooling and blood stasis, which could otherwise induce a veno-arteriolar reflex vasoconstrictor response.

**Near Infrared Spectroscopy (NIRS):**a. Additional non-invasive studies relating to muscle physiology, tissue oxygenation and blood flow may also be assessed using near infrared spectroscopy (NIRS) methodologies. The red to nearinfrared (NIR) part of the electromagnetic spectrum (600 to 1000 nm) allows photons to penetrate a few centimeters below the surface of the skin. These photons are non-ionizing and do not induce local heat. There are numerous FDA cleared clinical instruments in wide use that employ NIR light for non-invasive muscle and brain tissue oximetry. Quantitative optical spectroscopy in the NIR allows for safe, non-invasive measurements of the concentrations of blood, water, and lipids in tissues. Caliper measurements are used to measure the thickness of the skin to approximate tissue depth. We will use a number of different NIRS technologies to precisely and accurately characterize tissue metabolism, composition, and perfusion in subjects with SCD. These technologies, used in combination with non-invasive perturbations to evaluate vascular health (vascular occlusion challenge and respiratory challenge), are described below:

- b. Diffuse Optical Spectroscopic Imaging (DOSI): DOSI is a progression on continuous-wave NIRS techniques that utilizes a frequency-modulated light source that allows for quantitative measurement of blood, water, and lipid concentrations in tissues. DOSI requires more advanced hardware than traditional NIRS techniques but is similarly safe and non-invasive.
- c. pocketNIRS: This is a portable NIRS device developed by Hamamatsu Photonics in conjunction with the [name] lab. pocketNIRS consists of a control unit and 2 probes with 3 light emitting diodes (740nm, 800nm, 850nm) and can be controlled via cell phone. It measures changes in oxyhemoglobin, deoxyhemoglobin and total hemoglobin and also gives absolute measurement of tissue saturation.
- d. Laser Speckle Imaging (LSI): (LSI is a NIRS technology that is sensitive to flow. LSI consists of a coherent non-collimated light source (typically 785 nm) and a camera that images the illuminated tissue area. When biological tissue is illuminated with coherent light, an interference pattern will be formed at the detector, known as a speckle pattern. Blood flow speed affects the pattern captured by the camera and characterizing these changes in the pattern allows for a measurement of blood flow in the skin microvasculature.
- e. Affixed Transmission Speckle Analysis (ATSA) (trade name: FlowMet-R): FlowMet is the contact, transmission based equivalent of LSI. Within this device, the source and detector are on opposite sides of the finger. Light that shines through the finger or toe is picked up by the camera on the other side. Blood flow speed affects the pattern captured by the camera. Characterizing these changes in the pattern allows for a measurement of arterial blood flow within the finger or toe.
- f. Diffuse correlation spectroscopy (DCS): DCS uses a 785 nm coherent light source with a detector some distance away. DCS measures the temporal fluctuations of near-infrared (NIR) light to measure flow in the microvasculature at a single point.
- g. PeriFlux 6000 for microcirculatory blood flow assessments: The PeriFlux System 6000 device will be used for measuring microcirculatory blood flow and oxygenation in the limb and poses a

*Abbreviated Title: IQ in sickle cell disease*

*Version Date: May 5, 2023*

non-significant risk. Diffuse reflectance spectroscopy (DRS) and laser Doppler flowmetry (LDF) have been successfully integrated enabling accurate measurements of blood flow and oxygenation in the microcirculation. A dedicated fiber-optic probe that integrates the DRS and LDF modalities is required as well as an external light source.

h. Vascular Occlusion Challenge: Subjects will not have any active role in this challenge. A standard blood pressure cuff will be placed upon the limb (arm or leg) to be studied. Subjects may be asked to lie on a gurney or reclining chair for comfort and to keep the occluded limb stable. A DOS probe will be placed on the limb, and continuous measurements using the NIRS methodologies described above will be taken throughout the challenge. Additional optical probes may be placed on other tissue sites, such as the forehead or non-occluded limb. The FlowMet may be used on one of the fingertip/toe in order to monitor blood flow. If the subject does not tolerate limb cuff inflation, we may instead switch to performing a vascular occlusion challenge on the finger using a finger-sized cuff instead.

i. Respiratory Challenge: Subjects will be asked to a) pace their breathing according to a specific metronome-controlled rate or b) hold their breath for as long as they are able. Participants may be asked to lie on a gurney or reclining chair for comfort and to aid in reducing motion artifacts in data. An optical probe will be placed on at least one tissue site and will collect data continuously during paced breathing. To better understand how muscle oxygenation and blood volume changes during this challenge, additional optical probes may be placed over the top of other tissue sites (e.g. shin bone, abdominal adipose tissue, forehead, etc.). Data from these additional locations does not increase the risk to participants and only adds more physiological context to data from muscle locations.

### *8.2.2 Biospecimen Evaluations*

***Biological specimen collection and laboratory evaluations.*** In addition to the clinical blood samples, subject will have research bloods drawn within the blood withdrawal volume limits established by the Clinical Center. RBC structure and functional studies, Flow cytometry, Platelet studies, RNAseq, Immunoblotting, and cytokine profiling may be performed.

Table :3

Table of samples to collect at baseline and end of study (2 visits)				
Test/assay	Volume blood (approx.)	Type of tube	Collection point (+/- 72hrs)	Location of specimen analysis
Routine* 
 
Hepatic, Mineral and Acute care panel
 
LDH, T. protein, CK, uric acid
 
C-reactive protein
 
B-type natriuretic peptide
 
Beta HCG (Female only)
 
	4 mL	LtGrnPSTGel (GLT) tube	Baseline (D0) and end of study D28)	Clinical Lab
Routine* 
 
CBC
 
Reticulocyte count
 
HPLC for Hb electrophoresis
 
Direct antiglobulin test (DAT)
 
	9ml (3 tubes)	EDTA tube	Baseline (D0) and end of study D28)	Clinical Lab
Routine* 
 
PT
 
PTT
 
INR
 
Fibrinogen
 
D-dimer
 
	3ml	3.8% Sodium Citrate	Baseline (D0) and end of study D28)	Clinical Lab
Biochemical studies** 
 
Soluble P-selectin
 
Plasma PDI activity assay
 
Protein Carbonylation state (Western Blot)
 
	3 ml	3.8% Sodium Citrate	Baseline (D0) and end of study D28)	NHLBI Sickle Cell Branch, Sickle Thrombosis Lab
Coagulation studies** 
 
Microparticles/EVs
 
Prothrombin fragment F1.2, Thrombin anti-thrombin complexes (TAT)
 
	3 ml (1 tube)	3.8% Sodium Citrate	Baseline (D0) and end of study D28)	NHLBI Sickle Cell Branch, Sickle Thrombosis Lab

*Abbreviated Title: IQ in sickle cell disease*

*Version Date: May 5, 2023*

Red Blood Cell studies** 

• Deformability

• Oxygenscan

• Aggregation

• ROS production

• PS and PDI exposure and distribution (FACS)

	6 ml (2 tubes)	EDTA tube	Baseline (D0) and end of study D28	NHLBI Sickle Cell Branch, Sickle Thrombosis Lab
Platelet function tests** 

• Studies of platelet aggregation and platelet dependent thrombin generation

	6 ml (2 tubes)	3.8% Sodium Citrate	Baseline (D0) and end of study D28	NHLBI Sickle Cell Branch, Sickle Thrombosis Lab
Leukocytes isolation for gene expression and RNAseq** 

• Monocyte TF gene expression

• Tissue factor RNAseq

• Complement variants

• P-selectin variants

	5 ml (1 tube)	EDTA	Baseline (D0) and end of study D28	NHLBI Sickle Cell Branch, Sickle Thrombosis Lab
Contact Pathway	6 ml (2 tubes)	3.8% Sodium Citrate + Corn Trypsin Inhibitor (CTI)	Baseline (D0) and end of study D28	NHLBI Sickle Cell Branch, Sickle Thrombosis Lab

\*Tests necessary for routine care of patient with sickle cell disease.

\*\*Research blood samples to be collected at baseline during study enrollment and during follow up.

### *8.2.3 Correlative Studies for Research/Pharmacokinetic Studies*

N/A

### *8.2.4 Samples for Genetic/Genomic Analysis*

The mononuclear cell fraction will be isolated and stored for gene expression and RNAseq specifically looking at tissue factor expression in monocytes and gene variants involving thrombo-inflammatory pathways (P-selectin and the complement).

*Abbreviated Title: IQ in sickle cell disease*

*Version Date: May 5, 2023*

### **8.3 SAFETY AND OTHER ASSESSMENTS**

Physical examination, laboratory tests and adverse event review will be assessed at baseline and at 4 weeks.

Safety, tolerability and adherence assessments will be performed at baseline and at 4 weeks and whenever clinically indicated.

Counseling: Subjects should maintain a stable diet and not start any new diet or active SCD treatment for the duration of the study.

24-hour Dietary Recall: At three timepoints throughout the study, trained nutrition staff from the NIH CC will collect a 24-hour recall to reflect dietary intake from the prior day with nutrition staff entering information directly into Nutrition Data Systems for Research software (NDSR, University of Minnesota, Minneapolis, MN) to obtain nutrient and dietary quercetin intake data.

Participants experiencing adverse events after the start of IQ/placebo up until 4 weeks after discontinuation, may have a clinic visit for assessment and will be managed as clinically indicated. All patients will receive a phone call study visit 4 weeks after IQ/placebo discontinuation to assess for AEs.

### **8.4 ADVERSE EVENTS AND SERIOUS ADVERSE EVENTS**

#### *8.4.1 Definition of Adverse Event*

Adverse event means any untoward medical occurrence associated with the use of an intervention in humans, whether or not considered intervention-related (21 CFR 312.32 (a)).

#### *8.4.2 Definition of Serious Adverse Events (SAE)*

An adverse event (AE) or suspected adverse reaction is considered "serious" if, in the view of the investigator, it results in any of the following outcomes: death, a life-threatening adverse event, inpatient hospitalization or prolongation of existing hospitalization, a persistent or significant incapacity or substantial disruption of the ability to conduct normal life functions, or a congenital anomaly/birth defect. Important medical events that may not result in death, be life-threatening, or require hospitalization may be considered serious when, based upon appropriate medical judgment, they may jeopardize the participant and may require medical or surgical intervention to prevent one of the outcomes listed in this definition. Examples of such medical events include allergic bronchospasm requiring intensive treatment in an emergency room or at home, blood dyscrasias or convulsions that do not result in inpatient hospitalization, or the development of drug dependency or drug abuse.

#### *8.4.3 Classification of an Adverse Event*

##### *Severity of Event*

This study will utilize the Common Terminology Criteria for Adverse Events version 5.0 (CTCAE v5.0) for toxicity and adverse event reporting. A copy of the CTCAE v5.0 can be downloaded from the [https://ctep.cancer.gov/protocolDevelopment/electronic\\_applications/ctc.htm](https://ctep.cancer.gov/protocolDevelopment/electronic_applications/ctc.htm).

*Abbreviated Title: IQ in sickle cell disease*

*Version Date: May 5, 2023*

AEs will be recorded, verified, and followed until satisfactory resolution or stabilization. In the event of any treatment related SAEs, enrollment will be suspended until discussed with the IRB and Clinical Director.

#### *8.4.4 Grading and attribution of adverse events*

Severity definitions found in the CTCAE v5.0 will be used for grading the severity (intensity) of AEs:

- 1) **Mild:** Asymptomatic or mild symptoms; clinical or diagnostic observations only; intervention not indicated.
- 2) **Moderate:** Minimal, local or noninvasive intervention indicated; limiting age-appropriate instrumental ADL\*.
- 3) **Severe:** Severe or medically significant but not immediately life-threatening; hospitalization or prolongation of hospitalization indicated; disabling; limiting self-care ADL\*\*.
- 4) **Life- threatening:** Life-threatening consequences; urgent intervention indicated.
- 5) **Death:** Death related to AE.

\*Instrumental ADL refer to preparing meals, shopping for groceries or clothes, using the telephone, managing money, etc.

\*\*Self-care ADL refer to bathing, dressing and undressing, feeding self, using the toilet, taking medications, and not bedridden.

#### *8.4.5 Relationship to Study Intervention*

- All adverse events (AEs) must have their relationship to study intervention assessed by the investigator or designee who examines and evaluates the participant based on temporal relationship and his/her clinical judgment. The degree of certainty about causality will be graded using the categories below. In a clinical trial, the study product must always be suspect.
- **Definitely Related** – There is clear evidence to suggest a causal relationship, and other possible contributing factors can be ruled out. The clinical event, including an abnormal laboratory test result, occurs in a plausible time relationship to study intervention administration and cannot be explained by concurrent disease or other drugs or chemicals. The response to withdrawal of the study intervention (dechallenge) should be clinically plausible.
- **Probably Related** – There is evidence to suggest a causal relationship, and the influence of other factors is unlikely. The clinical event, including an abnormal laboratory test result, occurs within a reasonable time after administration of the study intervention, is unlikely to be attributed to concurrent disease or other drugs or chemicals, and follows a clinically reasonable response on withdrawal (dechallenge).

- **Potentially Related** – There is some evidence to suggest a causal relationship (e.g., the event occurred within a reasonable time after administration of the trial medication). However, other factors may have contributed to the event (e.g., the participant’s clinical condition, other concomitant events). Although an AE may rate only as “possibly related” soon after discovery, it can be flagged as requiring more information and later be upgraded to “probably related” or “definitely related”, as appropriate.
- **Unlikely to be related** – A clinical event, including an abnormal laboratory test result, whose temporal relationship to study intervention administration makes a causal relationship improbable (e.g., the event did not occur within a reasonable time after administration of the study intervention) and in which other drugs or chemicals or underlying disease provides plausible explanations (e.g., the participant’s clinical condition, other concomitant treatments).
- **Not Related** – The AE is completely independent of study intervention administration, and/or evidence exists that the event is definitely related to another etiology. There must be an alternative, definitive etiology documented by the clinician.

#### *8.4.6 Expectedness*

The PI or designee will be responsible for determining whether an AE is expected or unexpected. An AE will be considered unexpected if the nature, severity, or frequency of the event is not consistent with the risk information previously described in the Investigator’s Brochure for IQ.

We expect some vasovagal symptoms during blood draws (expected frequency 50%) and transient bruising at the site of blood draws (expected frequency 50%). Approximately 20% of SCD patients may experience a vaso-occlusive pain crisis “acute crisis” as part of their underlying disease, thereby resulting in hospitalization and reporting of SAEs.

#### *8.4.7 Time Period and Frequency for Event Assessment and Follow-Up*

The occurrence of an adverse event (AE) or serious adverse event (SAE) may come to the attention of study personnel during study visits and interviews of a study participant presenting for medical care, or upon review by a study monitor.

Investigators will assess the occurrence of AEs and SAEs at all patient evaluation time points during the study. Grade 2 and above adverse events plus grade 2 laboratory abnormalities associated with clinical signs or symptoms whether volunteered by the patient, discovered by study personnel during questioning, or detected through physical examination, clinically significant laboratory test, or other means will be recorded on the appropriate CRF. Information to be collected includes event description, date of onset, clinician’s assessment of severity, relationship to study product (assessed only by those with the training and authority to make a diagnosis), and date of resolution/stabilization of the event. AEs collected for the purpose of the study will be documented appropriately regardless of relationship to the IND agent. AEs will be followed to adequate resolution or stabilization or until V4 (phone call).

The following AEs will not be captured in the research database:

- Grade 1 adverse events

*Abbreviated Title: IQ in sickle cell disease*

*Version Date: May 5, 2023*

- Grade 2 laboratory abnormalities not associated with clinical signs or symptoms.

SCD is a chronic disease associated with recurrent acute painful crises and this information will be documented in the medical record. Any medical condition that is present at the time that the participant is screened will be considered as baseline and not reported as an AE. However, if the study participant's condition deteriorates at any time during the study, it will be recorded as an AE. Changes in the severity of an AE will be documented to allow an assessment of the duration of the event at each level of severity to be performed. AEs characterized as intermittent require documentation of onset and duration of each episode.

The PI or designee will record all reportable events (those entered in the research database with **start dates** occurring any time after the study intervention has started until 7 days (for non-serious AEs or SAEs) after the last day of administration of the study supplement. At each study visit, the team member will inquire about the occurrence of AE/SAEs since the last visit. Events will be followed for outcome information until resolution or stabilization or until V4 (phone call).

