### 1.3 SCHEDULE OF ACTIVITIES (SOA)

EVALUATION AND ASSESSMENTS	Screening (A)	Baseline	End of Study	Phone Call (B)
PROTOCOL TIMEPOINT VISITS	1	2	3	4
Days		D0	D28	D56
Window +/- days	-90Days	-28Days	+ 7Days	$\pm$ 7Days
Evaluations & Consent				
Consent to study	x			
Review Inclusion/Exclusion Criteria	x	x		
Review of Medical History	x	x	x	
Procedures & Assessments				
Establish Baseline Symptoms		x		
Physical Examination	x	x	x	
Review of Medications	x	x	x	
Vital Signs with Weight (kg)	x	x	x	
Review Of Adverse Events		x	x	x
24-hour Dietary Recall	x	x	x	
Peripheral Arterial Tonometry (PAT) (ENDO-PAT)		x 	x 	
NIRS (Near Infrared Spectrometry)		x 	x 	
CHEMISTRY LABS				
Female, Pregnancy Test, Beta HCG (blood or urine)	x 	x 	x 	
Acute Care Panel	x	x	x	
Mineral Panel	x	x	x	
Fasting Glucose	x			
Hepatic Panel	x	x	x	
Total Protein	x	x	x	
Creatinine Kinase	x	x	x	
Uric Acid	x	x	x	
C-Reactive Protein (hs-CRP)		x	x	
B-type natriuretic peptide (P-BNP)		x	x	
Lactate Dehydrogenase	x	x	x	
Calculated Creatinine Clearance	x	x	x	
Viral Serology: HIV, hepatitis B and C (Serum HBsAg, anti-HBc, anti-HBs, anti-HCV, anti-HIV)	x			
HEMATOLOGY LABS				
CBC with differential	x	x	x	
Hemoglobin Electrophoresis	x	x	x	
D-Dimer	x	x	x	
Coagulation Screen (PT, PTT, INR, Fibrinogen)	x	x	x	
Reticulocyte Count	x	x	x	
Direct Antiglobulin Screen		x	x	
Research Samples (Up to 30 mL)				
Biochemical Studies (3 ml 3.8% Sodium Citrate)		x	x	
Coagulation Studies (9 ml 3.8% Sodium Citrate)		x	x	
Red Blood Cell Studies (6 ml EDTA tube)		x	x	
Platelet Function Test (6 ml 3.8% Sodium Citrate)		x	x	

*Abbreviated Title: IQ in sickle cell disease*

*Version Date: May 5, 2023*

Leukocytes isolation for gene expression and RNAseq (3 ml 3.8% Sodium Citrate)		x	x
Study Supplement Medication			
Study Supplement Randomization		x	
Study Supplement, Diary and Electronic Pill Dispenser Dispensed		x 	
Study Supplement Compliance			x 
Study Supplement, Diary and Electronic Pill Dispenser Returned			x

A = Screening tests will be done at the Screening Visit unless any of the tests have been performed under another NIH protocol within 90 days prior to day 0 of study drug.

B. Any adverse event requiring a clinic visit during that safety follow up period will be managed as clinically indicated

x = for females of child bearing potential

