#### 9.3.1 *Evaluable for toxicity*

All patients randomized will be evaluable for toxicity from the time of their first treatment with study supplement or placebo until 28 days after completion of the end of study visit.

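### Protocol 8.4.7 records only events starting within 7 days of the last dose, which conflicts with the 28-day toxicity period in 9.3.1 and the day-56 safety call; one onset window should be set and used to define 'treatment-emergent'

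*Protocol*

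**What the plan says.** - **Recording rule (Protocol 8.4.7).** An event is entered in the research database if its start date falls after the intervention began and "until 7 days (for non-serious AEs or SAEs) after the last day of administration of the study supplement". The same limit is given for serious and non-serious events.
- **Evaluability (Protocol 9.3.1).** Randomised patients are evaluable for toxicity from first treatment "until 28 days after completion of the end of study visit".
- **Safety call (Protocol 8.3 and 1.3).** Section 8.3 states: "All patients will receive a phone call study visit 4 weeks after IQ/placebo discontinuation to assess for AEs". The schedule of activities marks the row "Review Of Adverse Events" at the day-56 call (plus or minus 7 days). Its footnote B adds: "Any adverse event requiring a clinic visit during that safety follow up period will be managed as clinically indicated". Section 8.3 also provides: "Participants experiencing adverse events after the start of IQ/placebo up until 4 weeks after discontinuation, may have a clinic visit for assessment".
- **Other text in 8.4.7.** "Investigators will assess the occurrence of AEs and SAEs at all patient evaluation time points during the study". The section also has staff ask at every study visit about events since the previous one, and treats worsening of a participant's condition at any point in the study as a recordable event. Its list of events left out of the database covers Grade 1 events and asymptomatic Grade 2 laboratory abnormalities. It does not mention late onset.
- **Tables (Protocol 9.4.4).** Treatment-emergent events are to be summarised overall, by relatedness, at Grade 3 or above, and where they led to stopping treatment. The abbreviation list spells the term out without defining it, and the SAP has no safety section.
- **Serious events (Protocol 8.4.9).** The investigator reports any serious event after the start of intervention to the sponsor, with no end date.

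**The concern.** Safety and tolerability are the second objective in the synopsis. Patients are described as evaluable for about eight weeks and are asked about new events at the end of that time. Yet the database rule would turn away a Grade 2 or higher event found at that call if it began more than 7 days after the last dose. A reader of the tables could take an absence of events to cover the whole evaluable period when it covers only part of it.

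The two periods also have different anchors. Recording runs from the last dose and evaluability from the end-of-study visit. Protocol 4.1 foresees participants who stop study drug early while the day-28 measurement is still sought. For them the recording period can close before that visit, at which the schedule calls for examination, laboratory tests and adverse-event review.

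**Working it through.** The plan gives no figure of its own here to reproduce. The check is day arithmetic on its stated periods.

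**Inputs**
- *L* = day of last dose. Dosing is 28 days, with up to 7 more if needed (Protocol 6.1.2 and 6.1.6).
- *V* = day of the end-of-study visit: day 28, window plus 7 days (Protocol 1.3).
- Recording closes at *L* + 7 (Protocol 8.4.7).
- Evaluability closes at *V* + 28 (Protocol 9.3.1).
- Call at day 56 plus or minus 7, so day 49 to day 63 (Protocol 1.3).

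**Formula.** Evaluable days outside the recording rule = (*V* + 28) − (*L* + 7).

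**Results**
- Nominal schedule, *L* = 28 and *V* = 28: 56 − 35 = 21 days, namely days 36 to 56. This is 21/56 = 37.5% of the evaluable period. If the 28th dose falls on day 27, the figure is 56 − 34 = 22 days.
- Dosing ends on day 28, visit on day 35: 63 − 35 = 28 of 63 days.
- Early stop, with an assumed last dose on day 6 and *V* = 28: recording closes on day 13, so 56 − 13 = 43 of 56 days.
- Recording closes before a day-28 visit whenever *L* + 7 < 28, that is *L* < 21.
- On the nominal schedule the call falls 49 − 35 = 14 to 63 − 35 = 28 days after recording has closed.

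**Which rule reaches the tables.** Section 8.4.7 is the only text that sets an onset limit for database entry. Under that rule the database holds no later-starting event, so the 9.4.4 tables cannot show one. Section 9.4.4 does not say that its tables stop there, and 9.3.1 implies that they do not.

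**Why this cannot be turned into events.** The documents give no rate of late-onset events and no frequency of early stopping. The roughly 20% crisis frequency in Protocol 8.4.6 has no stated time base. The figures above are calendar days only.

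**The case against.** The strongest reply is that 8.4.7 is explicit. It names a start, an end and a scope. The missing closing bracket in the sentence does not obscure its meaning and may come from the PDF conversion. Section 9.3.1 defines who is evaluable, not what is entered. Footnote B and the clinic-visit sentence in 8.3 concern management of an event. The call also has a purpose under the 7-day rule, because events that began in time are followed for outcome until then. The list introduced by "The following AEs will not be captured in the research database" is a filter on grade, so its silence on timing means little. On this view 8.4.7 already supplies a usable meaning for 'treatment-emergent', and only a cross-reference is missing.

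Much of this stands. A reader might infer that the documents leave the recording window open. They do not: 8.4.7 sets it, and the trouble is that other sections conflict with it. The reply does not remove that conflict. Section 8.3 gives the purpose of the call as assessing adverse events, and 8.4.7 itself requires questions about new events at each visit and recording of deterioration throughout the study. Nothing ties 9.3.1 or 9.4.4 to the 7-day limit.

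A reader might also infer that the arms would be recorded unequally, because the cut-off follows the last dose. The rule is the same in both arms of a double-blind trial and no early-stop rates are given, so this is not shown.

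**Conclusion.** The conflict is real and its consequence is modest. If 8.4.7 is followed as written, on the nominal schedule Grade 2 or higher events starting on days 36 to 56 are sought but left out of the 9.4.4 tables, while patients count as evaluable for that time. For participants who stop drug before day 21, recording ends before a day-28 visit. The day counts assume that visits fall on the stated days. The day-6 stop is an assumed example.

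Stronger conclusions are not supported. The primary P-selectin analysis and the sample size do not depend on this window, and no effect on the stopping rule is claimed. Late serious events are not lost to oversight, since 8.4.9 sends them to the sponsor without a time limit. What is at risk is their place in the research database and tables, together with that of non-serious Grade 2 or higher events. Safety is analysed descriptively and listed as exploratory in 9.4.3. The exclusion of Grade 1 events is a disclosed choice and is not at issue.

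**What to change.** Reconcile 8.4.7, 9.3.1 and 9.4.4 to one onset window, name its anchor (last dose, end-of-study visit or call), and use that window to define 'treatment-emergent'.

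- **Preferred:** enter Grade 2 or higher adverse events and serious adverse events with onset through the visit 4 call already scheduled. The anchor needs care for early stoppers: with a last dose on day 6, 8.3 puts the call at day 34 and the schedule of activities at day 56. The cost is some retrospective abstraction. The SAP reports 46 randomised and 45 in the analysis set, so up to 45 participants would need review of visit 4 and source records. The documents do not say how complete those records are, and uneven late capture would have to be disclosed.
- **Otherwise:** restate 9.3.1 and 9.4.4 as covering events only to 7 days after the last dose, and limit the safety statement to that period. This is a text change. Its price is a narrower safety claim.

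In either case, put the window in the table titles. Fix it before the final by-arm safety tables are produced. The unblinded statistician and the DSMB may already see events by arm, so the condition that matters is that the choice precedes those final tables. If that is no longer possible, report counts under both windows, which needs the same abstraction.
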